# All treatments will be administered in both eyes (OU).

# 3.4. Compliance

This study will be conducted in compliance with the protocol and in accordance with Good Clinical Practice (GCP), the ethical principles set forth in the Declaration of Helsinki, and with the United States (US) Code of Federal Regulations.

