#### Safety:

Safety measures are AEs, ocular tolerability, intraocular pressure (IOP), BCDVA, biomicroscopy, ophthalmoscopy, HR and BP, and subject questionnaire. Urine pregnancy tests for females of childbearing potential will also be conducted.

Measurements:

- Biomicroscopy, ophthalmoscopy, and HR and BP measured in accordance with the site's standard practice
- Ocular tolerability will be measured on a 4-point scale (0-3)
- Intraocular pressure will be measured with a Tono-Pen or Goldmann Applanation tonometry
- Subject questionnaire will be completed by the subject (Appendix 5 and Appendix 6)

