## 9. ASSESSMENT OF SAFETY

#### 9.1. Specification of Safety Parameters

The primary safety measures are subject-evaluated ocular tolerability and AEs. Other safety measures include biomicroscopy, ophthalmoscopy, BCDVA, IOP, subject questionnaire, and systemic safety (as measured by HR and BP). Urine pregnancy tests for females of childbearing potential will also be conducted.

The assessment of safety will be evaluated by:

- Ocular tolerability
- Biomicroscopy of the anterior segment including evaluation of lids, lashes, cornea, conjunctiva, iris, lens, and anterior chamber. Following topical fluorescein administration, the integrity of the cornea should be evaluated by fluorescein staining
- Ophthalmoscopy (direct or indirect) without dilation to evaluate the vitreous and posterior pole
- Best-corrected distance VA
- Intraocular pressure performed with a Tono-Pen or Goldmann Applanation tonometry
- Subject questionnaire
- Heart rate and BP (as per the site's normal equipment and procedures)
- Adverse events

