## **7.4. Planned Study Analyses**

### **7.4.1. Statistical Summaries: Descriptive and Inferential**

Categories for data presentation and analysis will consist of each treatment group: Nyxol and placebo for Stage 1, and Nyxol + LDP, Nyxol + LDP vehicle, Placebo + LDP, and Placebo + LDP vehicle for Stage 2.

All statistical tests will be two-sided and a difference resulting in a p-value of less than or equal to 0.05 will be considered statistically significant. The p-values for the analysis of secondary efficacy endpoints and safety endpoints will be considered descriptive, unless the endpoint is used for the hierarchical testing method. All p-values will be rounded to and displayed in four decimals. If a p-value less than 0.0001 occurs, it will be shown in tables as <0.0001.

Descriptive summaries of variables will be provided where appropriate. For continuous variables, the number of non-missing values (n), mean, standard deviation, median, minimum, and maximum will be tabulated by treatment group. For categorical variables, the counts and proportions of each value will be tabulated by treatment group. Expansion of descriptive table categories within each treatment may occur if such elaborations are thought to be useful.

All study-related data collected will be presented in listings. Study-related data not subject to analysis according to this plan will not appear in any tables or graphs but will be included in the data listings.

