**Table 3 Snellen Equivalents to VA Assessment Letters Read**

DCNVA/DCIVA letters	Snellen	BCDVA letters
≥75	20/15	≥60
70 - 74	20/20	55 - 59
65 - 69	20/25	50 - 54
60 - 64	20/32	45 - 49
55 - 59	20/40	40 - 44
50 - 54	20/50	35 - 39
45 - 49	20/63	30 - 34
40 - 44	20/80	25 - 29
35 - 39	20/100	20 - 24
30 - 34	20/125	15 - 19
25 - 29	20/160	10 - 14
<25	20/200	<10

Each of the continuous secondary efficacy endpoints will be analyzed using analysis of covariance (ANCOVA), with observed value as the dependent variable, treatment, [REDACTED] respective baseline value included as the covariate. Another ANCOVA will be applied with change from baseline as the dependent variable using the same factors and covariates.

The output from each ANCOVA will include the LSM and SE for all treatment groups, along with each LSM, the 95% CI and associated p-value for Nyxol vs. Placebo for Stage 1 time points, and Nyxol + LDP vs. Nyxol + LDP vehicle, Placebo + LDP, and Placebo + LDP vehicle for Stage 2 time points. [REDACTED]

For each of the secondary endpoints related to percent of subjects achieving certain criteria, the analysis will be performed using a logistic regression model with treatment and light/dark irides as factors, and the respective baseline as a covariate. For each analysis, the percentage

of subjects in each treatment group meeting the criteria will be presented, and the OR with 95% CI and p-value will be provided for Nyxol vs. Placebo for Stage 1 time points, and Nyxol + LDP vs. Nyxol + LDP vehicle, Placebo + LDP, and Placebo + LDP vehicle for Stage 2 time points. Categorical pupil diameter endpoints will be assessed using the study eye, fellow eye, and either eye, which is defined as achieving a given criterion in either eye.

In addition, each secondary efficacy endpoint will be [REDACTED].

Finally, select questions from the Subject Questionnaire will be analyzed. The results for Question 1 (change in near vision) and Question 5 (satisfaction with near vision) will be analyzed at Visit 2 (Stage 1 Day 8) and Visit 5 (Stage 2 Day 8) using an ANCOVA model with numeric observed response as the dependent variable ([REDACTED] and treatment as a factor. Only observed subject questionnaire data will be used; no imputation will be performed for missing data.

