## **10.3. Subjective Ocular Tolerability**

Results from the subjective ocular tolerability assessment, measured on a 4-point scale, will be summarized descriptively using counts and percentages for each treatment group at the 0 hour time point for each visit. Additionally, the categories “No Discomfort” and “Mild Discomfort” will be pooled into a single category and summarized descriptively, as will the categories “Moderate Discomfort” and “Severe Discomfort”.

Treatments will be compared for the two pooled categories using a Fisher’s exact test for Nyxol vs. Placebo for Stage 1 time points, and Nyxol + LDP vs. Nyxol + LDP vehicle, Placebo + LDP, and Placebo + LDP vehicle for Stage 2 time points. Separate summaries will be created for the study eye and the fellow eye.

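### SAP 10.3 analyses ocular tolerability by study eye and fellow eye only; the readable text names no worse-eye result per subject, and a one-eye rate can understate the share of subjects affected.

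*SAP*

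**What the plan says.** Protocol 9.1 gives the outcome its rank: "The primary safety measures are subject-evaluated ocular tolerability and AEs". Protocol 3.3 ends by stating that both eyes receive all treatments, and Protocol 5.1 sets a four-point tolerability scale.

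SAP 10.3 holds the analysis. Scores are to be "summarized descriptively using counts and percentages for each treatment group at the 0 hour time point for each visit". None and mild are pooled, as are moderate and severe. The inferential step is "Treatments will be compared for the two pooled categories using a" Fisher's exact test: Nyxol against placebo in Stage 1, and Nyxol + LDP against each of the other three arms in Stage 2. The section closes with "Separate summaries will be created for the study eye and the fellow eye". It mentions no either-eye, worse-eye or per-subject result.

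Protocol 10.3.6 asks only for a summary by arm at selected time points and does not say whether the unit is the eye or the subject.

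Elsewhere the SAP does combine the two eyes. In 9.1.2, "Categorical pupil diameter endpoints will be assessed using the study eye, fellow eye, and either eye, which is defined as achieving a given criterion" in at least one of the two eyes. In 10.1, a subject with several reports of the same adverse event is counted once.

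**The concern.** The safety question most readers will ask is how many subjects had moderate or severe discomfort. Both eyes are dosed, and a subject who is uncomfortable in one eye is an affected subject whichever eye carries the study-eye label. Under SAP 10.3 that subject is an event in one table and a non-event in the other, and neither table counts subjects affected in at least one eye.

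At stake is how a primary safety measure is described. A reader who takes the study-eye percentage as the subject percentage may read it too low, by an amount the tables do not show. In addition, each treatment contrast yields two p-values, with no statement of which one describes subjects.

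**Working it through.** The documents give no tolerability rate, no between-eye agreement and no power for this outcome, so there is no plan figure to reproduce. The group sizes are consistent: 320/4 = 80 per Stage 2 arm and 320/2 = 160 per Stage 1 group.

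**Step 1: what holds without assumptions.** Let p1 and p2 be the proportions of subjects with moderate or severe discomfort in the study eye and the fellow eye. Then

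P(either) = p1 + p2 − P(both),

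so max(p1, p2) ≤ P(either) ≤ min(1, p1 + p2). A one-eye rate is therefore never above the subject rate. It equals the subject rate only when no subject is affected in the other eye alone. Two separate tables give p1 and p2 but not P(both), so they only bound the subject rate: 10% in each eye is compatible with anything from 10% to 20% of subjects.

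**Step 2: size under assumed inputs.** Assume the same rate p in both eyes and a between-eye correlation phi. Then

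P(both) = p² + phi·p(1 − p), and P(either) = 2p − P(both).

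For p = 0.08, p² = 0.0064 and p(1 − p) = 0.0736. At phi = 0.3, P(both) = 0.0064 + 0.3 × 0.0736 = 0.0285, and P(either) = 0.16 − 0.0285 = 0.1315. The relative shortfall is 1 − 0.08/P(either). An 8% one-eye rate in an arm of 80 is 6.4 subjects.

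| phi (assumed) | Subject rate | Subjects in an arm of 80 | Relative shortfall of the one-eye rate |
|---|---|---|---|
| 0.3 | 13.2% | 10.5 | 39% |
| 0.5 | 11.7% | 9.3 | 32% |
| 0.7 | 10.2% | 8.2 | 22% |
| 0.9 | 8.7% | 7.0 | 8% |
| 0.95 | 8.4% | 6.7 | 4% |
| 1 | 8.0% | 6.4 | 0% |

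**Step 3: effect on the planned comparison.** Exact power of the two-sided Fisher test at 0.05, by enumeration, for assumed per-eye rates of 8% against 2%, with the same phi in both groups:

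| Outcome | 80 per arm | 160 per group |
|---|---|---|
| One eye | 26% | 62% |
| Either eye, phi 0.3 | 53% | 88% |
| Either eye, phi 0.9 | 30% | 67% |
| Either eye, phi 0.95 | 28% | 65% |
| Either eye, phi 1 | 26% | 62% |

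**Step 4: number of comparisons.** Tolerability is scheduled at Visits 1, 2, 4 and 5. That gives 1 + 1 + 3 + 3 = 8 contrasts, hence 16 tests by eye against 8 on a subject score.

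**Step 5: what each visit measures.** At Visits 1, 4 and 5 a drop is given at the site at the 0 hour time point. At Visit 2 no in-office dose is scheduled, and time 0 falls about 12 hours after the previous evening's home dose (Protocol section 5 and Table 1). The Visit 2 contrast therefore does not describe discomfort on a clinic-administered drop.

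**The case against.** **Agreement between eyes may be high.** Both eyes get the same product, so close agreement is plausible, and the gap is then small: 8.4% against 8.0% at phi 0.95, and nothing at phi 1. A reader might infer that every one-eye rate understates the subject rate, or that a 39% shortfall is to be expected. The documents support neither. With no concordance figure, the supportable statement is that a one-eye rate can understate and never overstates.

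**A reader might infer that the subject rate will never be reported.** That cannot be established. The list of planned tables (SAP 12.1) is redacted, as are the tolerability details in SAP 4.2.2 and 5.6, and SAP 9.1.2 shows that the plan leaves some detail to that list. By-subject safety listings are also planned, so the rate could be derived from them. What stands is narrower: the readable method text specifies by-eye results only, and no subject-level rate or comparison is prespecified there.

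**The testing argument carries little weight.** SAP 7.4.1 sets a 0.05 threshold but treats safety p-values as descriptive, and no significance decision rests on tolerability. The test count and the power figures bear on clarity and sensitivity, not on error control.

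**By-eye reporting is the SAP's habit for ocular safety.** IOP (10.5) and biomicroscopy and ophthalmoscopy (10.7) are handled the same way. The either-eye rule for pupil diameter belongs to an efficacy endpoint, so it is not a safety precedent that 10.3 contradicts, and Protocol 10.3.6 is not contradicted either. This is fair. Still, that rule shows the device is already in the plan, and discomfort is rated by the subject.

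**Subject-level ocular safety is not absent.** Adverse events are counted once per subject and tabulated by maximum severity (SAP 10.1). That does not replace a worse-eye tolerability score.

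**Conclusion.** The point holds in limited form. SAP 10.3 specifies a primary safety measure by eye only. The share of subjects with moderate or severe discomfort in at least one eye is not named in the readable text and cannot be recovered from the two by-eye tables.

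The direction of any gap is certain; its size is not. With an assumed 8% per-eye rate, the subject rate runs from 13.2% (phi 0.3) through 8.7% (phi 0.9) to 8.0% (full agreement). These figures rest on assumed and equal eye rates and an assumed correlation, and the low-correlation end should not be read as a forecast.

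This is a gap in safety reporting that is worth closing before unmasking. It touches no efficacy conclusion, analysis population or error rate.

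**What to change.** In SAP 10.3:

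- Define a subject-level tolerability score as the worse of the two eyes at each scheduled time point.
- Report, by treatment group, the number and percentage of subjects with moderate or severe discomfort in at least one eye.
- Run the planned Fisher comparison on that score, stating that its p-values remain descriptive.
- Keep the study-eye and fellow-eye tables as descriptive support.
- Add a note that the Visit 2 result reflects discomfort about 12 hours after a home dose, not on a drop given in the clinic.

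If the redacted table list already contains a worse-eye table, only the method text in 10.3 needs to be brought into line with it.

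The cost is one derived variable, one extra table and a few sentences. No new data are needed and trial conduct does not change.

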#### **10.4. Vital Signs**

Descriptive statistics of observed values will be presented for vital sign data at baseline, Visit 2 (Stage 1 Day 8) at the 12 hour post-dose time point, and Visit 5 (Stage 2 Day 8) at the 8 hour time point by treatment group. Changes from baseline to each time point will be presented.

#### **10.5. IOP**

Observed values and change from baseline in IOP at baseline, Visit 2 (Stage 1 Day 8) at the 12 hour post-dose time point, and Visit 5 (Stage 2 Day 8) at the 8 hour time point will be summarized for the study eye and the fellow eye by treatment group. Treatments will be compared using the same ANCOVA model proposed for the continuous secondary efficacy endpoints.

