# Pilocarpine Hydrochloride

A detailed report of pilocarpine, its product label, properties, and potential risk are provided in the IB (2022).

Pilocarpine hydrochloride (PCH) has been studied in a prior clinical trial by Ocuphire. In addition, there is a recently approved PCH drug at 1.25% and extensive literature on pilocarpine's ability to reduce PD across various concentrations. These pupil-constricting effects, however, are counteracted by a dose-dependent side effect profile, notably browache and stinging in the eye upon topical application of the drug.

In an effort to better characterize an efficacious dose of PCH that would have minimal side effects, Ocuphire conducted an expansive review of the medical literature concerning experiments of various doses of PCH and their effects on PD and side effect profile. Leavitt et al. found that normal pupils constrict with dilute concentrations of 0.25% and 0.125% pilocarpine (1.7 and 0.6 mm, respectively) but constrict insignificantly at concentrations of 0.0313% and 0.0625% (4). These decreases in PD were found to occur within 15 min of dosing, and peak pupil size reduction occurred at 30 to 60 min (4). On the other hand, 2% pilocarpine, although efficacious in decreasing PD by up to 3 mm, caused significant side effects, including worsened visual field and acuity (5).

When considering the effects on PD and the potential side effects of higher doses of pilocarpine, Ocuphire found that a range of 0.3% to 0.6% PCH may provide moderate efficacy with potentially limited side effects. Moreover, based on these data, Ocuphire has shown in its Phase 2 VEGA-1 study that the combination of Nyxol and LDP can have an additive to synergistic effect to produce a long duration of pupil reduction in an optimal range of PDs for treating presbyopia, without causing adverse side effects such as headache, browache, or accommodative spasm.

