Pilocarpine hydrochloride is the hydrochloride salt of (+)-pilocarpine (parent compound), a medication used to treat increased IOP, dry mouth, and presbyopia. Its chemical name is (3S,4R)-3-ethyl-4-[(3-methylimidazol-4-yl)methyl]oxolan-2-one hydrochloride, and it has a molecular weight of 244.72 g/mol. Pilocarpine hydrochloride is a hygroscopic, odorless, bitter-tasting white crystal or powder

The parent (+)-pilocarpine is a natural alkaloid extracted from plants of the genus *Pilocarpus* with cholinergic agonist activity.

The properties of PCH are described in Table 4.

Table 4:Pilocarpine H	ydrochloride Drug Substance and Drug Product Identifiers
Established name	Pilocarpine hydrochloride – parent (+)-pilocarpine
CAS registry number	54-71-7 – parent 92-13-7
Chemical class	A cholinergic parasympathomimetic agent, pilocarpine predominantly binds to muscarinic receptors, thereby inducing exocrine gland secretion and stimulating smooth muscle in the bronchi, urinary tract, biliary tract, and intestinal tract. When applied topically to the eye, this agent stimulates the sphincter pupillae to contract, resulting in miosis; stimulates the ciliary muscle to contract, resulting in spasm of accommodation; and may cause a transitory rise in IOP followed by a more persistent fall due to opening of the trabecular meshwork and an increase in the outflow of aqueous humor.
Chemical name	(3S,4R)-3-ethyl-4-[(3-methylimidazol-4-yl)methyl]oxolan-2-one hydrochloride
	or (3S-cis)-2(3H)-Furanone, 3-ethyl-dihydro-4-[(1-methyl-1H- imidazol-5-yl)methyl] mono-hydrochloride
Molecular formula	$C_{11}H_{17}ClN_2O_2 - parent C_{11}H_{16}N_2O_2$
Molecular weight (g/mol)	244.72 – parent 208.261
Investigational product name/formulation	Low-Dose Pilocarpine Hydrochloride Ophthalmic Solution 0.4% (LDP)
	Aqueous isotonic solution, compounded by Pine Pharmaceuticals LLC and released by Iuvo BioScience LLC
Concentration active	0.4%

 Table 4:
 Pilocarpine Hydrochloride Drug Substance and Drug Product Identifiers

Drug used in compounding the investigational product	PILOCARPINE HYDROCHLORIDE 4% - pilocarpine hydrochloride solution/ drops NDC 61314-0206-15
Manufacturer drug product used for compounding	
Storage requirements	
	Stored in a secured location (locked) with no access for unauthorized personnel

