*Other design considerations:*

Study medications (Treatments 1 and 2) were each dosed as a single drop in each eye, with Treatment 1 dosed in the evenings near bedtime and Treatment 2 dosed in the mornings. Baseline for the study is defined as pre-treatment (prior to Time 0 min) at Visit 1 (Screening/Baseline).

During Visit 2 (Stage 1 Day 8), Time 0 min is defined as the timing of the first efficacy assessments at the visit, approximately 12 hours after dosing with Nyxol the previous night (12 hour post-dose timepoint). During Visits 4 and 5 (Stage 2 Days 1 and 8, respectively), Time 0 min is defined as the time of Treatment 2 administration.

The study eye is defined as

[REDACTED]

The study eye and fellow eye will both be evaluated at all assessments.

The schedule for assessments and timing of events is presented in Table 1.

AE, adverse event; BCDVA, best-corrected distance visual acuity; BP, blood pressure; DCNVA, distance-corrected near visual acuity; HR, heart rate; ID, identification; IOP, intraocular pressure; OD, right eye; OS, left eye; PD, pupil diameter; VA, visual acuity.

Study OPI-NYXP-301 Statistical Analysis Plan

2023-09-29

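### The only analysed IOP reading after LDP comes 8 hours after the drop, so the planned comparison cannot detect an early rise that has resolved by then

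*SAP*

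**What the plan says.** Protocol Table 4 (section 5.4.1) describes pilocarpine in the eye as an agent that "may cause a transitory rise in IOP followed by a more persistent fall due to opening of the trabecular meshwork".

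In the Stage 2 schedule (Protocol Table 2) the IOP row has one mark, in the last column: Visit 5 at 8 hours. Protocol 8.2.4, which lists the assessments for Visit 4 (the first LDP dose), does not include IOP. Protocol 8.2.5 lists IOP for Visit 5 without a time.

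SAP 10.5 follows this schedule. It uses baseline, Visit 2 at 12 hours after Treatment 1 (before any LDP), and one later reading: "Visit 5 (Stage 2 Day 8) at the 8 hour time point will be summarized for the study eye and the fellow eye by treatment". SAP 5.1 sets the clock for Visits 4 and 5: "Time 0 min is defined as the time of Treatment 2 administration".

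For the analysis, SAP 10.5 says: "Treatments will be compared using the same ANCOVA model proposed for the continuous secondary efficacy endpoints". Neither SAP 10.5 nor Protocol 10.3.6 plans a count of subjects whose IOP rose by a given amount. Under SAP 7.3.1, unscheduled readings are listed but not analysed for safety.

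**The concern.** The protocol describes an effect that changes direction over time: up first, then down for longer. The plan samples that course once, late, and compares arms on the mean. If the rise is over by 8 hours, the comparison has nothing to find. If the later fall is present by then, LDP could even look favourable on IOP.

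At stake is what the report can say. IOP is a listed safety measure and gets a between-arm model with a confidence interval and p-value. A reader who sees no difference could take it as evidence that LDP does not raise IOP. The primary efficacy endpoint is read 30 minutes after the LDP drop, so the efficacy claim rests on a period in which IOP is not measured at all.

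**Working it through.** **Is any early reading analysed?** The readings in SAP 10.5, set against LDP exposure:

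| Reading | Time since LDP drop |
|---|---|
| Baseline | before any LDP |
| Visit 2, 12 h after Treatment 1 | before any LDP |
| Visit 4 | no IOP scheduled |
| Visit 5, 8 h | 8 h |

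Protocol Table 2 has 14 time columns across Visits 4 and 5, and the IOP row is marked in 1 of them. Time points at 0.5, 1, 3 and 5 hours exist at both visits but carry no IOP reading. Other rows of the table are redacted; the IOP row is visible and agrees with SAP 10.5.

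**Inputs for an illustration.** The plan gives no power, SD or margin for IOP, so there is no figure to reproduce.
- From the documents: about 80 subjects per Stage 2 arm (320/4) and a two-sided 0.05 level (SAP 7.4.1).
- Assumed: a mean rise of D (in SD units) at 1 hour after the drop, exponential decay with half-life h, no later fall, and a two-sample t-test in place of the ANCOVA.

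**Formula.** From 1 hour to 8 hours is 7 hours, so the difference left at 8 hours is D × 0.5^(7/h). Power is that of the t-test with noncentrality equal to this difference × √(80/2).

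| Half-life (h) | Share left at 8 h | Power at 8 h, D = 0.5 | Power at 8 h, D = 1.0 |
|---|---|---|---|
| 1 | 0.008 | 0.05 | 0.05 |
| 2 | 0.088 | 0.06 | 0.09 |
| 3 | 0.198 | 0.10 | 0.24 |
| 4 | 0.297 | 0.15 | 0.46 |
| 6 | 0.445 | 0.29 | 0.80 |
| 8 | 0.545 | 0.40 | 0.93 |

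Measured at 1 hour, power would be 0.88 for D = 0.5 and about 1.00 for D = 1.0. The result at 8 hours therefore depends almost entirely on a duration that the documents do not give. A later fall would push the 8-hour difference the other way.

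**What the 8-hour reading can do.** The difference detectable with 80% power is SD × √(2/80) × (1.960 + 0.842). For an assumed SD of 2, 3 or 4 mmHg that is 0.89, 1.33 or 1.77 mmHg. The reading is adequate for a sustained shift.

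**Means and individual rises.** Suppose 5% of one arm rose by 10 mmHg (assumed) and the rise was present when measured. The mean shifts by 0.05 × 10 = 0.5 mmHg, and power on means is 0.24, 0.15 or 0.11 for an SD of 2, 3 or 4 mmHg, after allowing for the extra spread that the rises cause. The chance of at least one such subject among 80 is 1 − 0.95^80 = 0.98. A count shows such cases far more readily than a test of means.

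**The case against.** The strongest reply is that the documents do not show that a rise will be missed. Table 4 says only that one may occur, in a general description of the drug and not of the 0.4% strength. The only timing figure for pilocarpine, "peak pupil size reduction occurred at 30 to 60 min", concerns the pupil, in a cited study of weaker solutions. This stands. A reader might infer that the comparison is bound to miss an early rise, but with a 6-hour half-life a 1.0-SD rise would still be found with power 0.80.

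The plan also shows more than means. SAP 7.4.1 tabulates median, minimum and maximum, all safety data are listed by subject, safety p-values are descriptive, and AEs are sought at each visit. This stands in part. A large individual change at 8 hours would appear in the maximum, but all the IOP output comes from the same late reading, and AE questioning would not find a rise without symptoms.

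No visible text plans to conclude that IOP is unaffected, and Protocol 9.1 places IOP among the other safety measures, behind tolerability and AEs. That limits the harm. It also makes a scope statement easy to accept.

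Two further inferences are tempting. The first is that heart rate and blood pressure share the problem, because SAP 10.4 also uses "Visit 5 (Stage 2 Day 8) at the 8 hour time point by treatment group". No passage describes an early heart rate or blood pressure effect of LDP, and Protocol 3.1 reports no clinically meaningful vital-sign changes with Nyxol. The second is that the angle-closure risk named in Protocol 3.2 applies here; that sentence concerns the approved 1.25% product.

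**Conclusion.** The point holds in a limited form. The sole analysed post-LDP reading is at 8 hours, the protocol itself describes a transitory rise before a fall, and so the planned ANCOVA is uninformative about a rise that has resolved by 8 hours. A null or negative result would not be evidence that no rise occurred.

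The size of the problem cannot be fixed from the documents. The power figures rest on an assumed rise, SD and exponential decay and serve only to show the range: for a 1.0-SD rise, from 0.05 at a 1-hour half-life to 0.93 at 8 hours. The cause lies in the protocol's Stage 2 schedule, which the SAP follows. SAP wording can prevent a wrong conclusion but cannot supply early data.

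**What to change.** In SAP 10.5, before unmasking:

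1. State that the Stage 2 comparison addresses IOP at 8 hours after LDP only and will not be used to conclude that LDP does not raise IOP. Cost: one sentence.
2. Add, by arm, the number and percent of subjects whose IOP rose from baseline by at least pre-specified amounts in either eye, with 95% confidence intervals for the differences, as a descriptive summary. Thresholds of 5 and 10 mmHg are examples; the documents give none, so the sponsor should confirm them. Cost: one table. On the 8-hour reading alone, this addresses the dilution of individual rises in the mean but not the timing.

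If Visit 5 data collection is still open, also amend Protocol Table 2 and SAP 10.5 to take IOP at an existing early post-LDP time point, after that time point's acuity and pupil measurements. At the 1-hour point, for example, the 30-minute primary reading would be untouched. Later acuity readings would then follow tonometry, as they already do at Visit 2, where IOP is taken at 0 hours. If the reading is moved and not added, the only 8-hour, end-of-study IOP is lost; adding it avoids that at the cost of one more procedure. This step may come too late: SAP 5.1 describes parts of the conduct in the past tense, which suggests but does not prove that visits were well advanced. In that case the report should say that IOP in the first hours after LDP was not assessed.
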